4.2 Exclusion Criteria

- Patients with prior use of home or office-based destructive treatments for this wart(s) in the last 1 month with SA or cryotherapy
- Immunoadjuvant therapy for warts in the last 4 months (e.g. Candida)
- History of vitamin D injection of warts ever
- High-dose vitamin D supplementation (>4,000 IU daily or equivalent) in the preceding 3 months
- Pregnancy or lactation
- Facial or genital warts
- Lesions not felt by the examining clinician to be a wart (e.g., corns or calluses)
- Immunosuppression (to include immunosuppressive medications or conditions as judged by the physician evaluating the patient at the baseline visit).
- Allergy to sesame oil

4.3 Subject Recruitment, Enrollment and Screening

- From the Principal Investigator or Co-Investigator clinical practices
- Information that is to be given to potential subjects (flyers)
- Advertisement on Mayo Classifieds and/or internet website posting
- Screening requirements/Evaluation and documentation of inclusion/exclusion criteria
 - If subject is an adult and has a wart on their skin
 - Wart is not located on face or genitals
 - Subject has not been treated with destructive treatment like Compound w or similar products or freezing spray in the last month
 - Subject has not had injection therapy into the wart in the last 4 months
 - Subjects has not been using high does vitamin D (more than 4,000 IU daily) in the last 3 months
 - Subject is not pregnant or breast-feeding
 - Subject does not have any immune suppressing disease or is on immune suppressing medications
 - Subject is not allergic to sesame oil

4.4 Early Withdrawal of Subjects

The subject may decide to withdraw at any time. Subjects should tell the Principal Investigator if they decide to withdraw early and they will be advised whether any additional tests need to be done for their safety.

4.4.1 When and How to Withdraw Subjects

Study subjects will be withdrawn for any subject who is intolerant of intralesional injections or has an adverse reaction to include infection, persisting pain, substantial pruritus, malaise, myalgias, fever or any other systemic symptoms suspected of being related to the injections. The risk of these is very low.

Following each visit, there will be a one week follow up survey of post-injection symptoms including pain, pain score, redness, swelling, itching and a one month follow up visit will be requested to examine and photodocument the injected wart. An additional survey will also be sent each week after to assess pain and pain score until the subject reports for 2 weeks without pain

The risk of hypervitaminosis D in subjects not taking high dose vitamin D with the low doses of 12,000 IU vitamin D3 that we are using in this study is negligible and will not be monitored. In the event of concern for adverse events in study participants (i.e., participant presents to ED with symptoms that may be consistent with Vitamin D toxicity such as confusion, polyuria, polydipsia, anorexia, vomiting, and muscle weakness or local inflammation at the site of injection) [name] will have 24/7 access to REDCap to break the blind and supply study drug administration information.

The study will be stopped for any unanticipated problems involving risks to subjects or others until these are understood and explained sufficiently to resume the study and for unexplained adverse outcomes or life threatening adverse events.

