multiplied by pi. Photos of the warts and size measurements of 2 wart diameters at 90 degree angles from each other will be collected at baseline and each subsequent visit and the measurements entered into an Excel spreadsheet to calculate surface area of each wart at each visit. Subjects with more than one wart will be given the choice of which wart they would like injected. Only one wart will be treated but the others up to 8 measured, photodocumented and observed for evidence of regression during the study. Confirmation of wart measurements by use of the PhotoExam images by study Co-I's blind to treatment and surface area calculations in Excel will be compared to those resulting from measurement at the time of the subject visits to ensure data integrity. The principle investigator will be responsible for ensuring data integrity by comparing measurements recorded at subject visits and measurements based on PhotoExam observations by the Co-I's for the first 3 subjects and then every 10th patient. Any discrepancy will result in an increase in monitoring and discussions with both observers to ensure consistency. Patients will return at a scheduled time to the ECH Procedure Clinic for injection and post-injection care and education as per the study schedule below.

Subjects will be contacted by email to complete a REDCap survey regarding side effects of treatment one week after each visit including pain, pain score, redness, pruritus, malaise, myalgia, and fever. These surveys will be reviewed weekly by the PI to ensure subject safety. In addition, subjects will be contacted by email to complete a REDCap survey regarding pain and pain score each week after the initial survey, until they report for 2 weeks without pain. This survey will also be sent to those subjects who do not receive an injection. They will be seen back 4 weeks and 8 weeks (+/- 1 week) after the first injection to receive an injection in the index wart if it is still present (subject may send a photo of their index wart to study coordinator to determine if the injection is needed so that medication can be ordered ahead of time), and to measure and photo-document all warts. Subjects will also be seen 12 weeks and 24 weeks (+/- 1 week) after the first injection to measure and photo-document all warts. Subjects will be questioned at each visit to ensure that they have not been using any other wart treatments.

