3.4 Primary Study Endpoints

Complete regression of index wart.

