4.4.2 Data Collection and Follow-up for Withdrawn Subjects

For all subjects, one week post-injection, follow up surveys (administered by study coordinators and completed/answered by subjects) will be reviewed weekly by the principle investigator. Additional surveys will be sent each week after until subject reports for 2 weeks without pain.

5 Study Drug

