7.1 Sample Size Determination

We can reasonably estimate an efficacy rate of up to 3 intralesional injections of vitamin D into recalcitrant warts as high as 90% for and as low as 40%. Given the study design of a dichotomous outcome as dependent variable of complete resolution of the wart(s) in the two groups to be compared – intervention and control - and an anticipated incidence of 5% spontaneous resolution of recalcitrant warts over the course of the 24 weeks of the study and an anticipated effect size of the intervention of 35% additional complete resolution based on the Abdel Kareem study with a Type I/II Error Rate alpha of 0.05 and power of 80%, we would need a sample size of 54 composed of 27 subjects receiving the intervention and 27 controls. We will increase enrollment to 30 in each group to account for drop outs. Since Abdel Kareem enrolled pediatric patients age 12 and older who tend to have a higher spontaneous resolution of warts than adults, we can reasonably base our sample size calculation on his study. If a high percentage of the patients we enroll have non-recalcitrant and non-plantar warts, we can assume a higher

spontaneous resolution rate but also anticipate a higher response to the intervention which will balance (e.g. sample size calculation for a 25% spontaneous resolution rate in previously untreated non-recalcitrant warts but a higher 60% response rate to vitamin D would give a same sample size calculation of 60 with 30 subjects in each arm)

Endpoints

Primary:

Complete regression of index wart.

Secondary:

Partial regression of index wart as measured in percent surface area lost.

Complete or partial regression of up to 7 other warts followed.

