7.2 Statistical Methods

Descriptive Statistics

There should be no significant temporal bias as season does not appear to affect wart refractoriness or resolution (though perhaps the increased vitamin D generated in skin in the summer would suggest a higher rate of spontaneous resolution if our hypothesis is correct). Secondary outcomes of partial resolution of warts based on visually and palpable size and photo-documented appearance will be recorded and reported as well. Fisher's exact test will be used to compare effects of placebo vs vitamin D3 injection on wart resolution.

Handling of Missing Data

Adherence to the protocol will be assessed by the study investigators through examination of data ensuring randomization and blinding, and self-reports of the study participants. Data from participants who for whatever reason deviate from the protocol will be handled by an intention to treat method in the final statistical analysis.

Primary Hypothesis: Vitamin D intralesional injection into cutaneous warts results in higher rates of complete resolution than saline placebo injection.

Fisher's exact test will be used to compare effects of placebo vs vitamin D3 injection on wart resolution.

Secondary Hypothesis

Partial regression of index wart as measured in percent surface area lost.

Multivariable linear regression will be used to assess the effect of vitamin D injection on final wart surface area, adjusting for initial surface area in the model.

Complete or partial regression of up to 7 other warts followed.

Fisher's exact test will be used to compare effects of placebo vs vitamin D3 injection on complete resolution of all additional warts. Multivariable linear regression will be used to assess the effect of vitamin D injection on final wart surface area of all additional warts, adjusting for initial surface area of the additional warts in the model.

Interim Analysis

The study dataset will be routinely monitored by the principle investigator and research coordinators to screen for any duplicate data entry and ensure sequential data input. Any adverse events or safety concerns will be immediately reported to the principle investigator and documented.

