7.3 Subject Population(s) for Analysis

- All-treated population: Any subject randomized into the study that received at least one dose of study drug

8 Safety and Adverse Events

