For this study, the study treatment follow-up period is defined as 112 days following the last administration of study treatment.

Preexisting Condition

A preexisting condition is one that is present at the start of the study. A preexisting condition should be recorded as an adverse event if the frequency, intensity, or the character of the condition worsens during the study period.

General Physical Examination Findings

At screening, any clinically significant abnormality should be recorded as a preexisting condition. At the end of the study, any new clinically significant findings/abnormalities that meet the definition of an adverse event must also be recorded and documented as an adverse event.

Post-study Adverse Event

All unresolved adverse events should be followed by the sponsor-investigator until the events are resolved, the subject is lost to follow-up, or the adverse event is otherwise explained. At the last scheduled visit, the sponsor-investigator should instruct each subject to report, to the sponsor-investigator, any subsequent event(s) that the subject, or the subject's personal physician, believes might reasonably be related to participation in this study.

Abnormal Laboratory Values

There will be no routine clinical laboratory monitoring for the purpose of this study. However, if subjects present with signs or symptoms of vitamin D toxicity to a medical care provider, values for standard laboratory workup including 25(OH) vitamin D concentration, calcium, phosphorus, creatinine would be monitored as well as any follow-up labs within the study's follow-up period.

A clinical laboratory abnormality will be documented as an adverse event if any of these values are found to be above normal ranges.

Hospitalization, Prolonged Hospitalization or Surgery

Any adverse event that results in hospitalization or prolonged hospitalization should be documented and reported as a serious adverse event unless specifically instructed otherwise in this protocol. Any condition responsible for surgery should be documented as an adverse event if the condition meets the criteria for an adverse event.

Neither the condition, hospitalization, prolonged hospitalization, nor surgery are reported as an adverse event in the following circumstances:

- Hospitalization for diagnostic or elective surgical procedures for a preexisting condition.

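### Subjects withdrawn for injection reactions are not clearly kept in the week 12 and 24 wart measurements, and no rule gives an outcome to an index wart left unmeasured

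*Combined protocol and SAP*

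**What the plan says.** **Withdrawal.** Section 4.4.1: "Study subjects will be withdrawn for any subject who is intolerant of intralesional injections or has an adverse reaction". The listed reactions include infection, persisting pain, substantial itching and systemic symptoms. The same section calls the risk very low. It also requests a one-month visit to examine and photograph the injected wart, but does not tie that visit to withdrawn subjects or to weeks 12 and 24.

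**Data after withdrawal.** Section 4.4.2, headed as covering withdrawn subjects, describes the one-week symptom survey and then: "Additional surveys will be sent each week after until subject reports for 2 weeks without pain". It mentions no wart measurement or photograph.

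**Scheduled outcome visits.** Section 3: "Subjects will also be seen 12 weeks and 24 weeks (+/- 1 week) after the first injection to measure and photo-document all warts". Withdrawn subjects are neither included nor excluded by name.

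**Analysis.** Under Handling of Missing Data, 7.2 says that data from participants who "deviate from the protocol will be handled by an intention to treat method in the final statistical analysis"; section 9.3 repeats this. The only population in 7.3 is "Any subject randomized into the study that received at least one dose of study drug". The primary endpoint in 3.4 is "Complete regression of index wart", with no visit named. The nearest thing to a time point is the control rate in 7.1, stated as "spontaneous resolution of recalcitrant warts over the course of the 24 weeks of the study".

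**The concern.** The withdrawal triggers are reactions to the injection, so any outcome lost through them is lost for a reason that may differ by arm. An unmeasured wart cannot be recovered later by any analysis.

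Loss can also run the other way. Section 1.3 reports, as anecdote from the institution's own Candida review, that some patients cancelled their last visit because their warts had gone. Dropping the missing is therefore not neutral, and neither is counting them as not cleared.

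The intention-to-treat sentence and the all-treated set settle who is analysed and in which arm. Fisher's test still needs cleared or not cleared for each subject. With no rule fixed, that choice could be made after the data are seen.

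**Working it through.** **Inputs.** 40 per arm (3.2); two-sided Fisher's exact test at 0.05 (7.1 and 7.2; two-sided is an assumption, supported by step 1); clearance of 40% vs 5%, or 60% vs 25% in the alternative scenario (7.1). The only loss allowance in the plan is the step from 27 to 30 per arm in 7.1, or 3 of 30. All loss counts below are assumptions.

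**1. The plan's own figure.** For 40% vs 5%, mean rate 0.225, two-sided 0.05, power 80%:

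n = [1.960·√(2·0.225·0.775) + 0.842·√(0.40·0.60 + 0.05·0.95)]² / 0.35² = 21.13.

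Continuity correction: (21.13/4)·[1 + √(1 + 4/(21.13·0.35))]² = 26.5, so 27 per arm, as stated. 27/0.90 = 30, so the allowance amounts to 10% in each arm.

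**2. One data set, two rules.** Suppose 6 vitamin D and 2 placebo subjects are unmeasured, leaving 34 and 38 observed.

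| Seen cleared | Missing dropped | Missing counted as not cleared |
|---|---|---|
| 17 vs 9 | 17/34 vs 9/38, p = 0.028 | 17/40 vs 9/40, p = 0.094 |
| 17 vs 10 | 17/34 vs 10/38, p = 0.052 | 17/40 vs 10/40, p = 0.155 |
| 20 vs 9 | 20/34 vs 9/38, p = 0.004 | 20/40 vs 9/40, p = 0.019 |
| 20 vs 10 | 20/34 vs 10/38, p = 0.008 | 20/40 vs 10/40, p = 0.037 |

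Only the first row changes conclusion. The last two rows are close to the counts expected at 60% vs 25% (34 × 0.60 = 20.4; 38 × 0.25 = 9.5), and there the rules agree. In the first row the extreme cases span 23/40 vs 9/40 (p = 0.003; missing vitamin D cleared, missing placebo not) to 17/40 vs 11/40 (p = 0.241; the reverse).

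**3. How often the rules disagree at 0.05.** Exact enumeration of binomial clearances among observed subjects, with loss unrelated to clearance:

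| Missing, vitamin D vs placebo | 40% vs 5% | 60% vs 25% |
|---|---|---|
| 4 vs 4 | under 0.1% | 0.6% |
| 3 vs 1 | 2.1% | 7.0% |
| 6 vs 2 | 3.9% | 17.2% |
| 2 vs 6 | 0.8% | 5.3% |

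For 6 vs 2, the chance of significance is 96.08% (dropped) against 92.20% (not cleared) at 40% vs 5%, and 82.35% against 65.11% at 60% vs 25%. The differences are 3.9 and 17.2 points, and every disagreement runs in that one direction.

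**The case against.** The strongest reply is that the follow-up gap is read from silence. Section 3 counts weeks 12 and 24 from the first injection and does not make those visits depend on further injections. Section 4.4.1 does ask for a wart photograph at one month. The intention-to-treat sentence covers deviation for any reason, and 7.3 retains every dosed subject. This stands to the extent that a reader who infers that the protocol ends wart follow-up at withdrawal, or removes withdrawn subjects from the analysis, goes beyond the text. It does not close the gap. The one-month visit does not secure weeks 12 and 24, the section meant for withdrawn subjects asks only for surveys, and none of these sentences assigns an outcome.

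The second reply concerns size. The plan allows for equal loss and calls reactions very unlikely, and one more placebo clearance removes the reversal in step 2. This stands. A reader might take the 60% vs 20% itching and pain in the single-blind saline-controlled trial described in 1.3 as the imbalance to expect. That trial used a different dose and a saline control, so it shows only that unequal reactions are plausible.

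A reader might also cite 8.1, where "the study treatment follow-up period is defined as 112 days following the last administration of study treatment", as evidence that observation ends early after an early stop. That is an adverse-event period; it does not govern wart visits and adds nothing here.

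Finally, counting every wart unmeasured at one named visit as not cleared would discard a clearance documented at an earlier visit. This is right, and the choice of scoring rule is a trade-off.

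**Conclusion.** The point holds as an ambiguity that should be fixed. The plan does not say whether a subject withdrawn for a reaction stays for the week 12 and 24 measurements, and it retains such subjects in the analysis without giving them an outcome. The absence of a scoring rule is certain from the text; the loss of follow-up is one reading of unclear wording.

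The consequence is small if losses are few or balanced (under 1% disagreement with 4 vs 4 missing). It matters mainly if losses are unequal and the effect is moderate (3.9% and 17.2% with 6 vs 2 missing at the two sets of rates in 7.1). Those figures assume the loss counts and assume that loss is unrelated to clearance. They do not show that the trial's result will be biased or reversed.

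**What to change.** **Main change.** Leave the criteria for stopping injections as they are. State in 4.4.1 and 4.4.2 that subjects who stop injections remain in the study and are invited to the already scheduled week 12 and 24 measurements and photographs, unless they withdraw consent. The cost is protocol wording and a few visits already in the schedule.

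**In support, before unblinding.** Name the visit at which the primary endpoint is read. Pre-specify one scoring rule for an index wart unmeasured at that visit, saying how a clearance documented earlier is used. Add three sensitivity analyses: available cases only; missing vitamin D cleared with missing placebo not cleared; and the reverse.

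**What the rule costs.** With missing counted as not cleared and 40 per arm, using effective rates p × (1 − loss), Fisher power is:

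| Loss, vitamin D vs placebo | 40% vs 5% | 60% vs 25% |
|---|---|---|
| none | 97.3% | 86.2% |
| 10% vs 10% | 94.9% | 78.1% |
| 15% vs 5% | 91.6% | 64.3% |
| 7.5% vs 2.5% | 95.1% | 76.5% |

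Dropping the missing (34 vs 38 analysed) keeps 96.1% and 82.4%, but relies on loss being unrelated to outcome. The last row shows the gain if retention halves the unequal loss, which is why the follow-up wording comes first.

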4.4.2 Data Collection and Follow-up for Withdrawn Subjects

For all subjects, one week post-injection, follow up surveys (administered by study coordinators and completed/answered by subjects) will be reviewed weekly by the principle investigator. Additional surveys will be sent each week after until subject reports for 2 weeks without pain.

5 Study Drug

5.1 Description

Most pharmacologic data relates to oral dosing of vitamin D3. Studies have found that healthy adults reach 25(OH)D3 plasma concentrations of about 20 ng/mL with oral dosing of 600 to 800 IU vitamin D per day.^{24,25} Other studies have found that a high single dose of 150,000 IU orally raises serum 25(OH)D peaking to 139.0 nmol/l at day 7 then slowly declines, while subjects taking 5,000 IU daily peaks to high of 130.5 nmol/l, with no clinical significant elevations in calcium or phosphorus in daily or single high dose regimens.²⁶

5.2 Treatment Regimen

Cholecalciferol (Vitamin D3), injection of 0.3 ml 40,000IU, intralesional (specifically at the base of the wart with needle centered under the wart) at baseline visit and weeks 4 and 8 as needed.

5.3 Method for Assigning Subjects to Treatment Groups

The research pharmacy will perform the randomization and assign a number associated with a specific treatment drug.

5.4 Preparation and Administration of Study Drug

Subjects will be randomized to receive an intralesional (specifically at the base of the wart with needle centered under the wart) injection of 0.3 ml of cholecalciferol (vitamin D3) in sesame oil 40,000 IU/mL prepared from a fresh 1.5 ml vial and the unused portion of the vial discarded. These injections will be provided in an exam room near the ECH Procedure Clinic on Baldwin 4. Controls will receive 0.3 ml of a similarly clear and equally viscous solution of sesame oil packaged in the same appearing vials. The wart to be injected will be sprayed for a few seconds until it turns white with ethyl chloride to reduce discomfort of the injection. Injections of 0.3 ml will be performed using a 3/4" 30 g needle on a Luer-lock 1 ml syringe under the center of the wart being treated avoiding entering the skin from more than one entry point, repositioning the needle tip if liquid runs out from under the wart or from the wart as it is being injected. Any escape of injectate during the injection will be recorded. A Band-Aid will be applied and participants instructed to remove it after 1 hour unless there is continued bleeding. Vials will be ordered from the pharmacy as required for investigational medications for each individual patient and picked up by study coordinators from the pharmacy. These vials will either contain active drug (vitamin D3 in sesame oil) or placebo (sesame oil), randomization performed by the pharmacy. A spreadsheet will be completed for each study subject who arrives at the procedure clinic to record patient study number, Mayo Clinic number, vial A/B (or however pharmacy

chooses to identify study drug vs placebo) used, any escape during injection of injectate, and pain score immediately, 1 minute and 5 minutes after injection.

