5.8 Masking/Blinding of Study

The pharmacy will prepare a stock of vials of vitamin D3 and placebo at intervals when requested. At their subsequent visit, participants will receive the same vial containing the same unknown as they received at their prior visit.

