8.2 Recording of Adverse Events

At each contact with the subject, the study team must seek information on adverse events by specific questioning and, as appropriate, by examination. Information on all adverse events should be recorded immediately in the source document, and also in the appropriate adverse event section of the adverse event worksheet. All clearly related signs, symptoms, and abnormal diagnostic, laboratory or procedure results should be recorded in the source document.

All adverse events occurring during the study period must be recorded. The clinical course of each event should be followed until resolution, stabilization, or until it has been ultimately determined that the study treatment or participation is not the probable cause. Serious adverse events that are still ongoing at the end of the study period must be followed up, to determine the final outcome. Any serious adverse event that occurs during the Adverse Event Reporting Period and is considered to be at least possibly related to the study treatment or study participation should be recorded and reported immediately.

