8.4 Unmasking/Unblinding Procedures

In the event of concern for adverse events in study participants (i.e., participant presents to emergency department with symptoms that may be consistent with vitamin D toxicity such as confusion, polyuria, polydipsia, anorexia, vomiting, and muscle weakness or local inflammation at the site of injection) [name] will have 24/7 access to REDCap to break the blind and supply study drug administration information. Documentation of this will be kept in the subject's source document.

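### The only vial code that section 5.4 names for the clinic log is a shared A/B code, and no section requires subject-unique codes; under a one-code-per-arm scheme, one code break could reveal the arm of every logged subject.

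*Combined protocol and SAP*

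**What the plan says.** Section 5.4 describes a spreadsheet completed for each subject who attends the procedure clinic. Its purpose is "to record patient study number, Mayo Clinic number, vial A/B (or however pharmacy", and the sentence continues "chooses to identify study drug vs placebo) used, any escape during injection of injectate, and pain score immediately". The code therefore sits in the same row as the patient's identifiers. A/B is the only scheme named, the choice is left to the pharmacy, and any alternative is described by its power to separate drug from placebo.

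The other sections that bear on vial codes say the following.

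- Section 5.3: the research pharmacy randomizes and will "assign a number associated with a specific treatment drug". Whether that number is unique to a subject is not stated.
- Section 5.4: vials are ordered patient by patient and "picked up by study coordinators from the pharmacy". No label format is given.
- Section 5.8: stocks of both products are prepared, and "participants will receive the same vial containing the same unknown as they received at their prior visit". No labelling rule is given.
- Section 5.9: product is obtained on prescription. Again no code format is given.
- Section 9.4: individual code numbers apply to subject information, not to vials.

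On unblinding, section 4.4.1 (repeated in 8.4) says that a designated role "will have 24/7 access to REDCap to break the blind and supply study drug administration information" when an adverse event in a participant raises concern. Section 8.4 adds: "Documentation of this will be kept in the subject's source document". Section 6.1 tells subjects that the study team will learn assignments only when the study ends.

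**The concern.** In a two-arm trial a code shared by everyone in an arm has a known weakness: the blind for all subjects hangs on one piece of information. A proper emergency unblinding of one subject then tells anyone who holds the log what both letters mean. With a code unique to each subject, the same event reveals one assignment.

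The blind matters here because the primary endpoint is complete clearance of the index wart, and deciding that a wart has gone involves some judgement. The principal investigator or co-investigators confirm measurements from photographs while blinded (sections 3 and 9.3). Coordinators collect the vials (5.4) and may receive a photograph used to settle whether another injection is needed (3, 6.3). No section withholds the log from these roles.

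The code-break route is not confined to rare systemic toxicity: the triggers listed in 4.4.1 and 8.4 include inflammation at the injection site. Documentation of a break is filed in the subject's source document, and under 8.2 "Information on all adverse events should be recorded immediately in the source document" as well. The plan does not say whether the break documentation states the arm.

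**Working it through.** The plan gives no figure on this point, so there is none to reproduce. The check is a reading of the text followed by a count.

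**Step 1. Is a subject-unique vial code required anywhere?** Sections 4.4.1, 5.3, 5.4, 5.7 to 5.9.4, 8.4 and 9.4 cover randomization, labelling, packaging, dispensing, masking, unblinding and record coding. None requires one. The number in 5.3, the ordering in 5.4 and the prescription in 5.9 are compatible with unique codes, but equally compatible with a shared code.

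**Step 2. What does one break reveal to a person who learns its result and sees the log?** Inputs: N = 80 (section 3.2) or N = 30 + 30 = 60 (section 7.1), with two arms. The plan gives both totals, so both are carried. Each subject keeps the same product throughout (5.8), so under A/B the subject's letter does not change.

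- One code per arm: knowing one letter gives the other by elimination. Subjects decoded = N = 80 or 60. Others exposed = N − 1 = 79 or 59.
- Subject-unique code: subjects decoded = 1, which is 1/80 = 1.25% or 1/60 = 1.7%. Others exposed = 0.
- Intermediate case (assumption: four codes, two per arm, used equally): decoded directly = N/4 = 20 or 15.

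**Step 3. How many assessments could be affected?** The counts in step 2 are ceilings. If m of the N subjects have had all their assessments when the break occurs, at most N − m can still have an assessment biased by it. The full N is reached only if the break precedes every subject's last assessment.

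**Step 4. What has to happen for harm?** Four things, none of which the documents establish: the pharmacy uses one code per arm; a break occurs; its result reaches someone beyond the designated role; and that person sees the log and influences an assessment. The documents give no rate for any of these, so no probability and no shift in the endpoint can be derived.

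**The case against.** The strongest reply is that A/B is a placeholder. Section 5.4 leaves the scheme to the pharmacy, section 5.3 speaks of a number and not a letter, and patient-level ordering and prescription dispensing look like patient-specific supply. Code formats are often set in pharmacy working documents that are not part of this plan. This stands as far as it goes: the documents do not show that a shared code was chosen, and if codes are unique the excess exposure is zero. It does not close the gap, because the protocol names only the weaker scheme and nothing in it rules that scheme out.

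A second reply is that unblinding is already contained. Access belongs to one designated role, a break is triggered by one participant's event, and photographic confirmation is described as blinded. That also stands in part. Under a shared code, however, a disclosure meant for one subject cannot be kept to one subject for a person who has the log.

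A third reply is that the endpoint is well protected by two perpendicular diameters, photographs at each visit with a ruler beside the wart, and blinded confirmation. These do limit the scope for bias. A reader might infer that the endpoint is a bare visual impression with no record behind it; sections 3 and 9.3 contradict that.

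**Conclusion.** The point holds as a conditional one. The plan names a shared two-level code as its only example and does not require subject-unique vial codes. If one code per arm is used, a single emergency break could reveal up to 80 (or 60) assignments instead of 1 to anyone who learns the result and also sees the log, and only assessments made after the break could be biased.

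A reader might go further and infer that the protocol mandates A/B, that the trial has been or will be unblinded, or that all 80 outcomes are at risk. The documents do not support any of these. The scheme is left to the pharmacy; no break or leak is described; the sections do not say who completes the log, who measures at visits, or whether a break note states the arm; and assessments completed before a break cannot be influenced by it. This is an open and avoidable risk to the blind, of unknown probability. It is worth closing because closing it costs little.

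**What to change.** - **Section 5.4:** replace the A/B entry and its parenthesis with a unique, non-informative subject or kit number.
- **Sections 5.3 and 5.8:** state that no vial code is shared between subjects, and that only the research pharmacy and the designated code-break role hold the list linking numbers to treatment.
- **Section 8.4 (optional):** state that a break discloses only the arm of the subject concerned. This is a clarification, since a break is already triggered by one participant's event.

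The cost is minor pharmacy labelling and log work, with no added subjects, visits or procedures. If the pharmacy already uses unique codes, the change only writes down current practice.
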